We aim to improve the treatment of PTSD using a combination of virtual worlds and neuro-feedback. Virtual worlds have been used to successfully treat PTSD induced by combat experience for a subset of the population. The primary approach is called extinction therapy, in which carefully controlled stimuli is used to evoke the associative memory of the original trauma. By maintaining the intensity of the patient response at a level the patient can comfortably tolerate, the sensitivity for triggering the traumatic response as well as the strength of the response can be gradually reduced with repeated treatments. However, given the variety of patient responses, modulating the stimulus optimally over the course of a treatment session is elusive. What is required is a real-time neuro-feedback system that can continually measure the degree of traumatic state of the patient, and then automatically control the stimulus to maintain the stress response within an effective therapeutic range. The purpose of this pilot project is to approach this goal by applying recent basic research we have conducted jointly at UT Austin and BCM on analyzing brain states using fMRI data with machine learning algorithms while exposing the subject to real-time virtual worlds. This pilot will extend that work to real-time neurofeedback applied to treatment of PTSD. Using fMRI for neuro-feedback, rather than the much more common EEG, should enable a significantly increased accuracy in the assessment of the patient; s current neuro-cognitive state. It should also lead to a better understanding of the neurophysiology during a stress response, e.g. which brain regions are most involved. This is not necessarily the same as which brain regions are the most active. Our analysis technique takes the next step by measuring the degree to which brain regions are critical to discriminating between different brain states, such as threatened versus safe.

Section E: Protocol Risks/Subjects

E1. Risk Category

Category 1: Research not involving greater than minimum risk.

E2. Subjects

Gender:

Both

Age:

Adult (18-64 yrs)

Ethnicity:

All Ethnicities

Primary Language:

English

Groups to be recruited will include:

Patients

Which if any of the following vulnerable populations will be recruited as subjects?

Mentally ill

Vulnerable populations require special protections. How will you obtain informed consent, protect subject confidentiality, and prevent undue coercion?

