Patients will be assessed by a clinician as competent and stable enough to understand and sign the consent form, to be exposed to a virtual world with war scenes, and to be scanned in an MRI machine.

Informed consent will be obtained according to federal regulations and BCM policies. The investigational nature and objectives of the trial, the procedures involved and their attendant risks and discomforts will be carefully explained to the patient prior to enrollment. Confidentiality will be protected within the limits allowed by law. It will be emphasized that the study is completely voluntary. Adequate time will be allowed to decide on their participation status. Questions and concerns will be addressed thoroughly.

E3. Pregnant woman/fetus

Will pregnant women and/or fetuses (as described in 45 CFR 46 Subpart B) be enrolled in the research? No

E4. Neonates

Will neonates of uncertain viability or nonviable neonates (as described in 45 CFR 46 Subpart B) be enrolled in the research? No

E5. Children

Will children be enrolled in the research?

Section F: Design/Procedure

F1. Design

Select one category that most adequately describes your research:

c) Pilot

Discuss the research design including but not limited to such issues as: probability of group assignment, potential for subject to be randomized to placebo group, use of control subjects, etc.

Subjects will be PTSD patients deemed stable enough to go through these procedures unharmed. There is no placebo group, and all patients will undergo similar protocols. All subjects will first be trained in the stimulus in an office equipped with the Virtual Iraq (software Bravemind or similar) stimulus equipment. This first session will establish stimulus criteria that will later be used during exposure to similar stimuli while being scanned with MRI. Subjects will be given real-time feedback during these sessions in an effort to train them to reduce their stress level. We hypothesize that this treatment will allow PTSD patients to learn how to bring their brain activity to a "non-threatened" state on demand, whenever they are confronted with stressful situations in real life.

Inclusion Criteria:

Adult veteran patients suffering from post traumatic stress syndrome as assessed by a clinician will be included. A score of 2 or 3 on the Clinician-Administered PTSD Scale (CAPS) will be required. For testing of procedures, healthy controls will also be included.

Exclusion Criteria:

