1. Claustrophobia (this would make lying in the scanner very uncomfortable). 2. Pregnant (the patient will be queried on pregnancy status at each visit, if patient reports being pregnant she will be discontinued from the study). 3. Contraindications to MRI: pacemaker, aneurysm clips, neurostimulators, cochlear implants, metal in eyes, steel worker, or other implants. 4. History of head injuries resulting in loss of consciousness > 30 minutes. Non-fit to be scanned for any other reason, as assessed by a psychiatrist. 5. A CAPS score or 0 or 1 (not enough symptoms to need treatment) or 5 (for possible safety reasons).

F2. Procedure

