J1. Waiver of Consent

Will any portion of this research require a waiver of consent and authorization? Yes

Please describe the portion of the research for which a waiver is required. (Example: chart review to determine subject eligibility)

A waiver of consent and HIPAA authorization are requested in order to conduct chart review to determine participant eligibility. Participant eligibility will be determined by presence or absence of current PTSD diagnosis. Chart review will only be conducted for study candidates whom have expressed interest in the study and have provided verbal consent to verify current PTSD diagnosis (yes/no) via medical chart review. Once a trained member of the study staff has confirmed the presence of a current PTSD diagnosis, we will move to informed consent for the study itself.

Explain why the research and the use or disclosure of protected health information involves no more than minimal risk (including privacy risks) to the individuals.

This research involves no more than minimal risk. Information obtained during chart review will not be recorded and will not affect participants enrolled in the study. Study candidates will be asked for verbal consent to verify that they have a current PTSD diagnosis (yes/no) via chart review.

Explain why the waiver will not adversely affect the privacy rights and the welfare of the research subjects.

The waiver will only be used to verify study candidates that have a current PTSD diagnosis (yes/no). Knowledge will be obtained by a trained member of the research staff that has pre-existing access to clinical records at the Michael E. Debakey VA medical center. This knowledge will not be recorded and will not affect the care of study candidates at the

Michael E. Debakey VA medical center. Study candidates will be asked for verbal consent to verify that they have a current PTSD diagnosis (yes/no) via chart review. Upon verifying that the interested study candidate has a current PTSD diagnosis (yes/ no), the study candidate will be contacted via phone by the same trained study staff member to schedule an in-person meeting with said study staff member to review the consent form for the current study.

Explain why the research could not practicably be conducted without the waiver and could not practicably be conducted without access to and use of the protected health information.

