Will this research require a waiver of the requirement for written documentation of informed consent? Yes

Explain how the research involves no more than minimal risk to the participants, and the specifics demonstrating that the research does not involve procedures for which written consent is normally required outside of the research context.

A waiver of consent will only be used to ask the study candidate a series of MRI safety questions and to determine whether the study candidate has a current PTSD diagnosis (yes/no). Only verbal consent will be used for that. Once we have demonstrated that it would be safe to scan a person, then we will move to informed consent for the study itself.

J2. Consent Procedures

Who will recruit subjects for this study?

PI

PI's staff

Describe how research population will be identified, recruitment procedures, any waiting period between informing the prospective participant and obtaining consent, steps taken to minimize the possibility of coercion or undue influence and consent procedures in detail.

PTSD patients will be identified by clinicians at MEDVAMC, who will refer them to the investigators of the study and their staff. Study candidates may indicate their interest in the study and sign up to be contacted for the study at VA sponsored research events. Study staff may access electronic medical records of interested study candidates to ensure PTSD diagnosis (yes/no). Then, study staff will contact interested study candidates via phone or in person to verify that subjects do not have any MRI contraindications. Subjects without MRI contraindications will then be consented during an initial screening session prior to beginning any virtual reality training. During the screening season, study staff will discuss study participation with subjects, including an explanation of the purpose, procedures, risks, benefits, and alternatives. Furthermore, study staff will answer any questions the subject may have prior to enrolling in the study and signing the consent form.

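### Does the single F1 sentence admitting healthy controls leave the entry rules, the 35 subjects or the primary CAPS comparison in doubt?

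*Combined protocol and SAP*

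**What the plan says.** - **F1, design prompt and answer.** The form asks the applicant to discuss, among other things, "potential for subject to be randomized to placebo group, use of control subjects, etc". The answer says "Subjects will be PTSD patients deemed stable enough to go through these procedures unharmed", states that there is no placebo arm, and does not mention controls.
- **F1, inclusion.** Adult veterans with clinician-assessed PTSD are eligible, and "A score of 2 or 3 on the Clinician-Administered PTSD Scale (CAPS) will be required". The next sentence reads "For testing of procedures, healthy controls will also be included".
- **F1, exclusion 5.** Among those excluded: "A CAPS score or 0 or 1 (not enough symptoms to need treatment) or 5 (for possible safety reasons".
- **E2.** Under "Groups to be recruited will include" the only entry is patients.
- **J1 and J2.** Once staff have checked the chart and one of them "has confirmed the presence of a current PTSD diagnosis, we will move to informed consent for the study itself". J2 adds that "PTSD patients will be identified by clinicians at MEDVAMC". Neither section mentions controls.
- **G1.** The number of subjects is 35 locally and 35 worldwide. G1 says no data existed from which to calculate a sample size.
- **F2 (data analysis paragraph) and G2.** The main question is whether PTSD symptoms fall over time, and the primary outcome is CAPS before and after the procedure. G2 also plans a general linear model on pooled imaging data to compare the Threat and Non-Threat brain states. It names no analysis population for either.

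**The concern.** Taken word for word, F1 admits healthy controls in one sentence, while its CAPS rules would turn away anyone with few or no symptoms. The design answer, written to a prompt that raises control subjects, is silent on them, and so are the recruitment and consent sections.

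Two things could be at stake. The first is eligibility: which criteria apply to a control. The second is the denominator. If controls count in the 35, fewer than 35 patients stand behind the before-after CAPS comparison, by an amount the reader cannot determine. If they do not count, the study enrols more people than G1 states. There is also a remote risk that someone pools controls into the CAPS analysis, where they have no PTSD symptoms to lose.

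**Working it through.** **1. Do the F1 sentences conflict?** The inclusion text runs in order: veteran patients with PTSD, the CAPS score required, then healthy controls who are also to be included, for testing procedures. The word for addition and the separate purpose make controls a second category. They are not patients who must also meet the CAPS requirement. Exclusion 5 explains the low-score exclusion by too few symptoms to need treatment, a reason that makes sense only for someone enrolled to be treated. H1 likewise applies its CAPS limit to patients. The most that can be said is that no exemption is written down.

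**2. Do E2, J1 and J2 rule controls out?** No. E2 is a form field listing groups. J1 concerns a waiver to check charts for a PTSD diagnosis, a step with no purpose for a healthy control. J2 describes how patients are found. Silence in these places is not a prohibition. The consent forms are not in the text available for review, so nothing can be inferred about how controls consent.

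**3. Can controls enter the primary analysis?** The stated question is whether PTSD symptoms decrease. No patient-control comparison is planned. An analyst would restrict the CAPS comparison to PTSD patients without being told. If controls were pooled by mistake, and their scores were near zero both times (assumed), the mean change would be multiplied by the patient share. With 5 controls in 35 that is 30/35 = 0.857, a dilution that cannot manufacture a benefit.

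**4. How much precision could be lost?** The figure of 35 cannot be reproduced, because G1 gives no inputs. As an illustration, take the 95% confidence interval for a mean paired change, in units of the SD of change:

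half-width = t(0.975, n − 1) / √n

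The numbers of controls are assumptions. All patients are taken to have both CAPS assessments.

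| Controls inside the 35 | Patients n | Half-width (SD) | Ratio to n = 35 |
|---|---|---|---|
| 0 | 35 | 0.3435 | 1.000 |
| 1 | 34 | 0.3489 | 1.016 |
| 2 | 33 | 0.3546 | 1.032 |
| 5 | 30 | 0.3734 | 1.087 |
| 6 | 29 | 0.3804 | 1.107 |
| 10 | 25 | 0.413 | 1.20 |
| 15 | 20 | 0.468 | 1.36 |

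For a handful of people used to test procedures, the widening stays below 10% up to 5 controls and passes it at 6. The 10% mark is only a yardstick; the plan has no such threshold.

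**5. If controls are outside the 35.** The patient number and the half-width of 0.3435 SD stand. Total enrolment then exceeds 35 by the number of controls, which affects the stated headcount and not the analysis.

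**The case for a change.** The best case for a change is that it costs almost nothing: delete one sentence, or add a few lines saying which entry criteria apply to controls and whether they count in the 35. No other section settles either point. F2 sends subjects through CAPS-5 screening, exposure and scanning with no separate path for controls. G1 asks for the number of subjects used in the study, and both readings of 35 remain open. The stated purpose of the controls also does not say whether their scans may enter the pooled general linear model.

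Most of this is factually right. The exemption is unwritten, the 35 is not split, and the imaging model has no named population. Nor do the documents prove that the number of controls is small; at 15 the interval would be 36% wider.

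What does not follow is that the result would be unsound. The imaging model is a further analysis meant to inform future therapy, with no decision attached to it. The number of patients actually analysed will be known and can be reported with the result, so a reader will see the precision achieved. How the CAPS limits are worded between F1 and H1 is a separate matter for the sponsor to reconcile and has no bearing on controls.

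**Conclusion.** The gap is real but clerical, and no change to the plan follows. Followed as written, the plan still gives a before-after CAPS comparison in PTSD patients, and controls have no role in it. The possible cost is some precision: between 1.6% and 8.7% on the confidence interval if 1 to 5 controls sit inside the 35, and none if they sit outside it, in which case the stated total is exceeded. A larger number of controls would cost more, but G1 describes a pilot with no power calculation and sets no target that could be missed.

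This rests on three assumptions: that controls serve only the purpose F1 gives them, that their number is modest (the documents do not state it), and that the analyst restricts the CAPS analysis to patients, as the stated question implies.

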Subjects will be first assessed and screened for eligibility and safety. As part of the screening process, a CAPS-5 PTSD clinician administered assessment will be administered. This administration may be recorded for validity purposes, in which chase data would be stored using a VA-approved secure portable USB device. These data will be destroyed at the conclusion of the study. Study participants will sign VA forms 10-3203 and 10-5345 for these purposes. The next step is an evaluation in a specially-equipped lab of appropriate stimulus parameters to evoke a stress response in each subject. The subject will interact with an audiovisual stimulus called Virtual Iraq, a commercially available virtual-world environment. The interaction involves passive view of a virtual town with an appearance similar to those found in Iraq. Events will occur in the stimulus designed to evoke stress, such as smoke, explosions, or the appearance of enemy combatants. The level of stress elicited by the virtual world will be manipulated using controls in the stimulus package specifically designed to vary threat levels. Patients will undergo this training in the presence of an experienced PTSD therapist, who will gradually guide the patient through a gamut of stress levels that remains at tolerable levels. Calm environments (such as a nice beach) will also be explored by the participants. Once we verify that all subjects can be safely exposed to this virtual world, they will be scanned using functional MRI under stimulus conditions that vary over a gamut of conditions varying from nonthreatening to strongly threatening. The MRI scanner we will use differs from conventional scanners only in that the magnet strength is 3 T, rather than the more typical 1.5 T magnets used in routine clinical scanning. The subject will enter a large room where a powerful magnet is located. Subject will be instructed to remove all jewelry and other metalcontaining objects. The subject will then be placed on a narrow table with plastic-encased metal coil close to the head. Next, the subject will be slid into a small tunnel approximately 6 feet long and 24 inches in diameter. The duration of the scan is approximately 70 minutes. A small mirror with a filter holder to enable 3D stimulation will be positioned above the subject's head so they can view a 3D LCD display at the opposite end of the scanner. After the subject is positioned, the table will move the subject into the scanner itself. Subjects will wear MR-compatible headphones for audio stimulation, and for voice-communication with a technician or investigator. They will also be given a pneumatic squeeze ball which they will instructed to use to signal that scanning should be stopped at any time. Subjects will participate in 3--8 scanning sessions. Brain imaging data will be collected and analyzed using machine learning techniques to discriminate a range of brain states varying from ¿non-threatening¿ to ¿highly threatening¿. The first 1--2 sessions will be used to ¿train¿ a software analysis program to recognize the subject; s brain states. Once these two states have been determined, subjects will be scanned during 1--6 feedback sessions, using similar stimulus conditions, but this time a "thermometer" will display, in real time, the current brain state threat level. Subjects will be instructed to use their mind to bring the thermometer toward the "non-threatening" state. Once the subject is able to move the thermometer toward sufficiently non-threatening "temperatures" the display will briefly change to a pleasing and comfortable image to provide positive feedback. Data storage in a VA repository will be a requirement of the study. Data will be stored in a VA repository (a folder within the S drive in which the imaging data will be stored) on the S drive. This repository is only not to lose data possibly necessary in the future analysis. It will not be released to other investigators unless thei have their own IRB approval prior to coming and asking for these data, including if the investigators of this study decide to do any further research unrelated to this study protocol. Participants will be free to withdraw their data from the study at any point.

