
Data analysis: During the training sessions we will use the imaging data in real time to feedback information about the brain state (where in a continuum from CALM to STRESS the participant is a each moment) for the participant to use mental strategies (think happy thoughts, breath deeply, imagine a quiet place, etc) to try to bring the thermometer toward CALM. As the thermometer moves to CALM, the environment will be manipulated toward less stressful images and sounds. We hypothesize that over time, participant's brains will accommodate to expect that these mental strategies effectively change the environment toward being calmer and safer. This may translate into such strategies becoming more and more useful in real life. The main data to be analyzed will be whether PTSD symptoms (as measured by questionnaires) decrease over time.

In an exploratory manner, some participants may explore the Virtual Iraq (and calm environments) while wearing a commercially available one-electrode eeg. This is similar to headphones and gives an eeg signal that will be analyzed to study the possibility of discerning the signal while under stress (Virtual Iraq) and calm epochs. This will last no more than 15 minutes and data will be analyzed for each individual, solely to verify feasibility for future studies.

Section G: Sample Size/Data Analysis

G1. Sample Size

How many subjects (or specimens, or charts) will be used in this study?

Local: 35 Worldwide: 35

Please indicate why you chose the sample size proposed:

There is no data available to calculate sample size. This will be a pilot to study the possibility that the proposed approach merits further study.

G2. Data Analysis

Provide a description of your plan for data analysis. State the types of comparisons you plan (e.g. comparison of means, comparison of proportions, regressions, analysis of variance). Which is the PRIMARY comparison/analysis? How will the analyses proposed relate to the primary purposes of your study?

The primary outcome will be clinical data from CAPS scores before and after the procedure.

In addition, we will use activity monitors (similar to a commercially available FitBit) that will be used by subjects from at least a week before the study starts, to at least a week after the last MRI session. This will allow us to study not only diurnal activity, but also quality of sleep, a major problem for PTSD patients.

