Finally, we will use general linear model analysis on aggregate data to determine if there are specific brain regions in which activity is higher or lower during the two brain states (Threat and Non-Threat). This data may render information important to design and improve PTSD therapy (pharmacological or otherwise) in the future.

Section H: Potential Risks/Discomforts

H1. Potential Risks/Discomforts

Describe and assess any potential risks/discomforts; (physical, psychological, social, legal, or other) and assess the likelihood and seriousness of such risks:

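### Threat level and audiovisual content change together, the decoder's label source is unstated, and nothing in the plan separates sensory content from stress

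*Combined protocol and SAP*

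**What the plan says.** F2 (Procedure) describes how threat is produced: "Events will occur in the stimulus designed to evoke stress, such as smoke, explosions, or the appearance of enemy combatants". It also says how threat is graded: "The level of stress elicited by the virtual world will be manipulated using controls in the stimulus package specifically designed to vary threat levels". Before any scan there is an "evaluation in a specially-equipped lab of appropriate stimulus parameters to evoke a stress response in each subject". In that same laboratory stage, "Calm environments (such as a nice beach) will also be explored by the participants".

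For the scanner phase, F2 says of the participants that "they will be scanned using functional MRI under stimulus conditions that vary over a gamut of conditions varying from nonthreatening to strongly threatening". The decoder's target is described in nearly the same words: "Brain imaging data will be collected and analyzed using machine learning techniques to discriminate a range of brain states varying from" non-threatening at one end to highly threatening at the other. The first one or two sessions train the software. One to six feedback sessions follow, with the decoded threat level shown as a thermometer.

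The data-analysis paragraph of F2 adds the feedback rule: "As the thermometer moves to CALM, the environment will be manipulated toward less stressful images and sounds".

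G2 (Data Analysis) plans a GLM of the pooled data. Its stated task: "determine if there are specific brain regions in which activity is higher or lower during the two brain states (Threat and Non-Threat"). Section D makes it a purpose of the pilot to measure how critical each brain region is to telling states such as threatened and safe apart.

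**The concern.** A decoder or a GLM contrast responds to anything that differs between the two conditions. Here threat is raised by putting more smoke, blasts and figures on the screen and more noise in the headphones. Visual and auditory cortex will follow those changes whether or not the participant is stressed. If nothing separates the two, a region can appear to distinguish threat from safety because of what it sees or hears.

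Two things are at stake. The first is the Section D aim of identifying which regions discriminate between the states. The second is the meaning of the thermometer. F1 hypothesises that patients learn to bring their brain activity to a non-threatened state at will. A falling thermometer is the natural evidence for that, but the scene itself becomes calmer as the thermometer falls.

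**Working it through.** The documents give no decoder accuracy, epoch count or GLM threshold, so there is no figure to reproduce. The check is a comparison of passages with a short piece of algebra.

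**1. What changes when threat changes.** By F2, the threat level is set through the stimulus software, so it changes only through what is shown and heard. This is true even inside a single virtual town, because explosions and their absence differ in sight and sound. The concern therefore does not depend on the beach scene.

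**2. Where the training labels come from.** The plan does not say. The stimulus condition is the only candidate described, and its wording nearly matches that of the brain states. The exploratory EEG sub-study does equate stress with Virtual Iraq, but that statement covers the EEG work only.

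**3. What could separate stress from content.** Four elements might help:

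| Element | Where | Linked to labels, decoder check or GLM? |
|---|---|---|
| Stimulus set individually to evoke stress | F2 | No. It sets intensity and does not separate stress from content |
| Threat graded by software controls | F2 | Not stated as the training contrast |
| Stress-response information gathered during scans | Section R, flyer | No. The measure is not named |
| Heart rate from wearable sensors | Section R, flyer | No |

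No sensory-matched condition and no covariate for sound or image content is described.

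**4. Consequence for the region map.** Let the response of region r be a_r × stress + b_r × sensory content + noise. Write ΔT and ΔS for the differences in stress and in sensory content between Threat and Non-Threat. Without a sensory term, the GLM estimates

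Contrast_r = a_r·ΔT + b_r·ΔS.

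- A purely sensory region (a_r = 0) still gives b_r·ΔS, which is not zero when ΔS is not zero.
- A purely stress-related region (b_r = 0) gives a_r·ΔT, as intended.

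The map can hold both kinds of region, and the reader cannot tell them apart. The same applies to a decoder trained on these conditions.

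**5. Consequence for feedback.** Write the thermometer reading as w_T × stress + w_S × sensory content. When the scene is made calmer, sensory content moves by ΔS and the reading moves by w_S·ΔS even if stress has not changed. A fall that occurs before the scene changes does not have this problem. Only the further fall does.

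**6. Primary outcome.** G2 compares CAPS scores before and after the procedure. Those scores are not computed from the decoder or the GLM, so this mechanism does not bias the comparison directly.

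**The case against.** A reader might infer that the decoder is trained on explosions against a beach. The documents do not support that. The beach sentence belongs to the pre-scan laboratory stage, and the scanner conditions name no beach. F1 says only that similar stimuli are used in the scanner. Nor do the documents state that brain states are defined by the scene; they leave the label source open.

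A reader might also conclude that the region analysis would return sensory areas. That goes too far: by step 4, stress-related regions can appear alongside sensory ones.

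The plan names no thermometer outcome, and the GLM is a secondary analysis in a declared pilot. F2 also describes feedback in two ways. One passage has similar stimulus conditions with a brief change to a pleasant image on success; the other has progressive change of the environment. These points limit the weight of the concern. They do not remove it, because region discrimination is a stated purpose in Section D and learned control is the hypothesis in F1. Under either description of feedback, what is displayed responds to the decoder.

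Healthy controls might be proposed as a check. F1 includes them only for testing procedures, and explosions may stress them too. Similar decoding in controls would therefore not show that the signal is sensory.

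**Conclusion.** The concern holds in a limited form. As described, threat level and audiovisual content are confounded, the label source is not stated, and no planned element separates the two. The decoder and the Threat versus Non-Threat map could partly reflect sensory content, and part of any thermometer fall after the scene changes may simply follow that change. This weakens the Section D aim and any claim of learned regulation. It does not directly bias the CAPS comparison.

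The size cannot be given, because the documents contain nothing from which the sensory share could be estimated. The conclusion rests on two assumptions: that displayed content differs between threat levels, which follows from F2, and that the stress-response and heart-rate data mentioned in the flyer are not already intended for labelling or validation, which the documents leave open.

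**What to change.** 1. State in F2 what supplies the training labels. If the in-scanner stress-response information is meant to label or validate the states, say so and name the measure. In the GLM and in the decoder evaluation, include sound level, luminance and motion of the displayed stimulus as nuisance regressors. Report results with and without them.
2. Where the training data allow, form the contrast from high and low threat settings within the same Virtual Iraq environment, not from different environments. This reduces the confound but does not remove it, so item 1 is still needed.
3. Base any statement about learned regulation on thermometer readings taken before the scene or display changes in response to the decoder. This restricts which readings are analysed and leaves the feedback procedure as it is. Holding the scene constant throughout would alter that procedure and is not needed here.

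**Cost.** This is mainly analysis work, plus a record of the displayed sound and images aligned with scan time. The sensory regressors are correlated with threat, so the adjusted contrast and decoder accuracy will look smaller and less precise. With correlation ρ between the threat regressor and the sensory regressors, the variance of the threat coefficient is multiplied by 1/(1 − ρ²) for a given residual variance. If ρ is close to 1, the data cannot separate stress from content, and the report should say so.
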